2.2 Secondary objectives

To compare the efficacy of naloxegol (with placebo) in critically ill adults initiated on scheduled IV opioids on each of the following outcomes:

During the period from time of scheduled opioid therapy initiation (IV fentanyl equivalent dose \geq 100 mcg/day) until ICU discharge, death or 10 days of study drug administration (whatever comes first):

(Note: there are up to three days to enroll and randomize subject after the initiation of scheduled opioid therapy).

- a. Incidence of lower GI tract paralysis (\geq 3 days without a SBM)
- b. Time to first SBM (in hours)
- c. Days without a SBM
- d. Average daily opioid requirement [in IV fentanyl equivalents (mcg)].

Note:

1. For the purposes of inclusion in the study, only opioids administered by the IV route will be considered but to calculate the daily opioid requirement all opioids administered (regardless of route) will be considered. All enteral/oral opioids will be reduced by 50% when converting to the IV fentanyl equivalent.
2. Administration of opioids will be mandated by the ICU team (as per routine clinical practice based on the ICU team evaluation of regular pain assessment scores) and will not be protocolized as part of the study.
3. While IV fentanyl is the most common IV opioid used in the medical ICU at Tufts MC, other opioids (e.g. IV and oral hydromorphone, oral oxycodone) are used at times. Choice of opioid during routine patient care is currently not protocolized in the ICUs at Tufts MC and will not be protocolized as a part of this study. The choice and amount of opioid administered each day will be collected as part of the study.

During the period from time of study enrollment (i.e., randomization) to ICU discharge, death or 10 days of study drug administration (whatever comes first):

- e. Time to first SBM
- f. Daily characterization of each SBM for size (small, medium or large)
- g. Daily characterization of each SBM for consistency (using the Bliss Stool Scale)
- h. Daily characterization of use of the study laxative guidelines.
- i. Daily volume of enteral nutrition administered.
- j. % of daily enteral nutrition goal met.
- k. Daily fluid balance (i.e., 24 hr ins and outs)
- l. Daily maximal pain scale score (using nurse-administered 10 point rating scale)

Drug Substance: Movantik
 Study Number: ESR-15-11000
 Tufts IRB #12043
 Version: Protocol version #19
 Date: September 10, 2018

- m. Daily Sedation Assessment Scale (SAS) score
 - a. Average

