12.2 Methods of statistical analysis

Baseline characteristics of patients will be compared using standard univariate methods (chi-square test, t-test) to confirm the randomization was successful in achieving comparable groups. To test the primary outcome (incidence of lower GI tract paralysis), given that there may be censoring (i.e., subject may die or withdraw from study before developing lower GI tract paralysis), we will present Kaplan-Meier curves for the naloxegol and placebo groups for the time to first development of lower GI tract paralysis (≥ 3 days without a SBM after study randomization) during the ICU stay up to 10 days and compare the curves using a log-rank test. If all subjects complete the study (e.g., no deaths, no withdrawal or loss-to-follow-up for other reasons), then we will instead compare the proportion of patients that develop lower GI tract paralysis after study randomization during the ICU stay up to 10 days between the naloxegol and placebo groups using a chi-square test. The secondary outcome, time to first SBM will be estimated using a Kaplan Meier time to event analysis and compared between groups using a log-rank test. The secondary outcome of the number of ICU days without a SBM will be compared between the naloxegol and placebo groups using the Poisson regression for count data and adjusting for total number of days in the ICU (up to a maximum of 10) as an offset term in the Poisson model. The secondary outcome of the average daily opioid requirements will be compared between groups using either a student t-test or nonparametric Wilcoxon rank-sum test if the assumptions of the student t-test fail to be met. Length of mechanical ventilation and ICU stay will be reported as medians and interquartile ranges and will be compared using the Wilcoxon Rank Sum Test. For all statistical tests of hypotheses, a two-sided p-value of ≤ 0.05 will be considered as statistically significant. As this is a Phase II proof of concept study a p value of <0.10 may still be worth consideration for future study, however. All statistical analyses will be performed using SPSS 17.0. (SPSS, Chicago, IL) or other comparable commercially available statistical software.

[figure not shown]

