Appendix 9. Daily Nursing Data Collection Form.

Subject ID: _____ Subject Initials: _____ ICU Room: _____ *Date (of day shift): _____ Study day# _____

*Note: this monitoring form goes from 07:00h to 06:59h the next day

Time of study drug administration : _____ h (note: should be around 0900h; if patient on tube feeds, please hold 1 hour before & after administration ; if patient is eating, administer 1 hour before or 2 hours after breakfast)

[Complete study drug administration instructions on next page]

Clinical Opioid Withdrawal Scale (COWS) Score to be completed 1 hour before and 2 hours after study drug administration (see next page)

Spontaneous Bowel Movements (from 0800h to 07:59h)	Time	Size (indicate small (S), medium (M) or large (L) (Use best judgment)	Bliss Stool Scale Score (see next page and on wall)	Comments
#1				
#2				
#3				
#4				
#5				
#6				
#7				
#8				

Does the patient have a urinary (foley) catheter in place for a clinical reason (s) Yes _____ No _____

Was the patient's ICU physician asked about whether the urinary (foley) catheter can be removed? Yes _____ No _____

Was the study laxative protocol utilized? Yes _____ No _____ If YES, which level? _____

Time frame	Day Shift (0700 – 14:59h)	Afternoon shift (15:00-22:59H)	Night shift (23:00-06:59h)
------------	---------------------------	--------------------------------	----------------------------

Drug Substance: Movantik
 Study Number: ESR-15-11000
 Tufts IRB #12043
 Version: Protocol version #19
 Date: September 10, 2018

Abdominal pressure score			
Time of evaluation			

For any questions regarding this study please page [name] or [name] at [name]

initials of investigational team member completing/verifying form _____ date _____

Clinical Opioid Withdrawal Scale (COWS) Score	1 hour before admin Time: _____	2 hours after admin Time: _____
Heart Rate: 0 = 80 bpm or below 1 = 81 to 100 bpm 2 = 101-120 bpm 4 = 121+ bpm		
Sweating over past ½ hour not accounted for by room temperature or patient activity: 0 = no chills or flushing 1 = patient reports chills or flushing 2 = flushed or observable moistness on face 3 = beads of sweat on brow or face 4 = sweat streaming off face		
Restlessness: 0 = able to sit or lie still 1 = patient reports difficulty sitting/lying still, but is able to do so 3 = frequent shifting or extraneous movements of legs/arms 5 = unable to sit/lie still for more than a few seconds		

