Appendix 10. Investigative Team Daily Data Collection Form.

IRB # 12043 Impact of Naloxegol (Movantik) on Prevention of Lower Gastrointestinal Tract Paralysis in Critically Ill Adults Initiated on Scheduled IV Opioid Therapy: A Randomized, Double-Blind, Placebo-Controlled, Phase II, Single-Center, Proof of Concept Study. PI: [name]

Subject ID: _____ Subject Initials: _____ ICU Room: _____ *Date (of day shift): _____ Study day# _____

*Note: this monitoring form goes from 0700h to 06:59h the next day

Time frame	Day Shift (0700 – 14:59h)	Afternoon shift (15:00-22:59H)	Night shift (23:00-06:59h)
Fentanyl (mcg)			
Hydromorphone (mg)			
Morphine (mg)			
Oxycodone (mg)			
Hydrocodone (mg)			
Methadone (mg)			
Other Opioids: Name and Dose			
Diazepam (mg)			
Lorazepam (mg)			
Midazolam (mg)			
Dexmedetomidine (mcg)			

Drug Substance: Movantik
Study Number: ESR-15-11000
Tufts IRB #12043
Version: Protocol version #19
Date: September 10, 2018

Propofol (mg)			
Haloperidol (mg)			
Quetiapine (mg)			
Volume of enteral nutrition administered (mL)			
Enteral nutrition goal (mL)			
% of enteral nutrition goal reached			
Fluid balance (+ or -) (mL)			
Lowest SAS			
Highest SAS			
ICDSC score (if evaluated during this shift)			
Lowest pain assessment score			
Highest pain assessment score			
Current Laxative Guideline Step (ie. 1, 2, 3 or 4)			
Laxatives administered (list all agents and doses)			
Requirement for mechanical ventilation? (Y/N)			
Presence of rectal tube? (Y/N)			

Drug Substance: Movantik
Study Number: ESR-15-11000
Tufts IRB #12043
Version: Protocol version #19
Date: September 10, 2018

(Please note time of insertion if new)			
GI or Surgical consult for lower GI tract paralysis? Y/N			
SOFA Score (worst values over study day)			
Serum creatinine (worst value over study day)			
Calculated creatinine clearance (worst value over study day)			

initials of investigational team member completing/verifying form _____ **date** _____

Daily SOFA Calculator

Pt Study ID: Pt Initials:

PP MM

Please retain this worksheet at the site with the CRF.

Calculate SOFA score using values from the 24 hour period prior to randomization.

A. Please circle appropriate score

Drug Substance: Movantik
 Study Number: ESR-15-11000
 Tufts IRB #12043
 Version: Protocol version #19
 Date: September 10, 2018

Organ System	0	1	2	3	4	Score
RESPIRATION PaO ₂ /FiO ₂ (mmHg)	>400	301-400	201-300	101-200 with respiratory support	< 100 with respiratory support	

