 Tufts operating room following emergency surgery	

Drug Substance: Movantik
Study Number: ESR-15-11000
Tufts IRB #12043
Version: Protocol version #19
Date: September 10, 2018

10. Prior ICU stay during this hospital admission: Yes No

If YES, specify unit: _____

11. Was a tracheotomy present on admission to ICU? Yes No

If YES, was it performed during this hospital admission? Yes No

12. Start date of mechanical ventilation: Date: ____/____/____ Time: ____:____ (24hr clock)

13. Admission APACHE III Diagnosis Code (Please see attached): _____

If "other" has been selected in any category, please specify: _____

14. APACHE II Score (Please see attached): Calculate APACHE II score using values from the 24 hour period prior to randomization.

APS: _____

Age Points: _____

Chronic Health Points: _____

Total APACHE II: _____

initials of investigational team member completing/verifying form _____ date _____

Drug Substance: Movantik
 Study Number: ESR-15-11000
 Tufts IRB #12043
 Version: Protocol version #19
 Date: September 10, 2018

Pt Number	Patient Initials	Date
____ / ____ / ____	____ - ____ - ____	

15. Baseline SOFA Score (Please see attached): Calculate SOFA score using values from the 24 hour period prior to randomization.

Total SOFA: ____

16. Last Spontaneous Bowel Movement (Per medical record review/family interview):

Date: ____ / ____ / ____

Time: ____ : ____ (24 hour clock)

17. Current infusions at randomization: (check all that apply)

Fentanyl:	 Yes	 No	Start date: ____ / ____ / ____	Time: ____ : ____	Rate: ____ mcg/hr
Hydromorphone:	 Yes	 No	Start date: ____ / ____ / ____	Time: ____ : ____	Rate: ____ mg/hr
Morphine:	 Yes	 No	Start date: ____ / ____ / ____	Time: ____ : ____	Rate: ____ mg/hr
Midazolam:	 Yes	 No	Start date: ____ / ____ / ____	Time: ____ : ____	Rate: ____ mg/hr
Lorazepam:	 Yes	 No	Start date: ____ / ____ / ____	Time: ____ : ____	Rate: ____ mg/hr
Propofol:	 Yes	 No	Start date: ____ / ____ / ____	Time: ____ : ____	Rate: ____ mcg/kg/min
Dexmedetomidine:	 Yes	 No	Start date: ____ / ____ / ____	Time: ____ : ____	Rate: ____ mcg/kg/hr

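### The nursing form's stool table runs on a different 24-hour day from the form itself, so stools timed 07:00 to 07:59 can be dated to either of two days

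*Protocol*

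**What the plan says.** The Protocol's Appendix 9 (daily nursing form) gives two different days on one page. The note at the top states that "this monitoring form goes from 07:00h to 06:59h the next day". The abdominal-pressure shift grid on the same page agrees with it, ending with "Night shift (23:00-06:59h". The stool table is headed "Spontaneous Bowel Movements (from 0800h to 07:59h". The form has a single "Date (of day shift" field. The stool rows have columns for time, size, Bliss score and comments, but none for date.

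Appendix 10, the investigators' daily form, uses the earlier day: "this monitoring form goes from 0700h to 06:59h the next day". It has no field for SBMs. The Appendix 9 table is therefore the only study form that captures on-study SBM times. By contrast, the baseline form in Appendix 11 gives both a date and a time field to the "Last Spontaneous Bowel Movement (Per medical record review/family interview" item.

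These times feed the primary analysis, "time to first development of lower GI tract paralysis" (Protocol and SAP, Section 12.2), where paralysis means at least 3 days without an SBM after randomization. They also feed the secondary outcome "Time to first SBM (in hours", days without an SBM (Section 2.2), and the safety definition of diarrhea as at least three loose or watery stools in 24 hours (Section 2.3). Section 11.1 refers back to Table 1 and the objectives for derivations. Nothing in either document says which window governs SBMs or how to date a stool passed between 07:00 and 07:59.

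**The concern.** The date of an on-study stool has to be inferred from the form's single date plus a clock time, and that inference depends on which window the reader applies. For one hour of the day the two windows give answers a full day apart. The primary outcome turns on whether a gap reaches 72 hours, so a 24-hour dating error is one third of the threshold. It can create or remove an event for a patient whose true gap is within a day of 72 hours. With 18 patients per arm, one reclassified patient is 1/18 = 5.6% of an arm.

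The printed instructions also leave room for a stool in that hour to be omitted or duplicated, because the old form has nominally ended and the new form's stool table has nominally not begun.

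**Working it through.** The plan states no figure on this point, so there is none to reproduce. The check compares the two windows and then scales the exposure.

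**1. The windows.** For a form dated day D:
- Form window: 07:00 on D to 06:59 on D+1, which is 1,440 minutes.
- Stool-table window: 08:00 on D to 07:59, read as the morning of D+1, which is also 1,440 minutes.

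Each window covers a full day, so either one used consistently loses nothing. Assigning every clock minute to D or D+1 under both windows gives the same day except from 07:00 to 07:59. That is 60 minutes, or 60/1,440 = 4.2% of the day. In that hour the form window implies D and the table window implies D+1, exactly 24 hours apart.

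**2. How an error arises in each direction.**
- A stool at 07:30 on D+1 is entered on form D, following the table heading, and later read by the form note. It is dated D, 24 hours too early.
- A stool at 07:30 on D is entered on form D, following the form note, and later read by the table heading. It is dated D+1, 24 hours too late.

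**3. Effect at the 72-hour threshold, for a first SBM.**
- Dated 24 hours late: a true time of 48 to 72 hours is recorded as 72 to 96, and a primary event is created.
- Dated 24 hours early: a true time of 72 to 96 hours is recorded as 48 to 72, and a primary event is removed.

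**4. Exposure.** The documents give no hourly distribution of stools, so uniform timing is assumed.
- If all 36 patients (Section 12.2.2) have a first SBM: 36 × 1/24 = 1.5 expected in the hour, and the chance of at least one is 1 − (23/24)^36 = 78%.
- If that hour holds half or twice its even share: 0.75 or 3.0 expected.
- Counting only first SBMs by day 4 at the planning rates (90% and 40% without one): 18 × 0.10 + 18 × 0.60 = 12.6 first SBMs, and 12.6/24 = 0.53 expected.

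**5. From exposure to a changed outcome.** An exposed first SBM changes the primary outcome only if it is also misdated, left uncorrected, and within 24 hours of the threshold on the relevant side. As an illustration with assumed values, one third in that band and one half misdated gives 1.5 × 1/3 × 1/2 = 0.25 expected changes, or about a 22% chance of any (1 − e^−0.25). With 0.2 to 0.5 in the band and 0.25 to 1 misdated, the range is 1.5 × 0.2 × 0.25 = 0.08 to 1.5 × 0.5 × 1 = 0.75. Gaps after the first SBM are not counted here.

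**6. After correction.** With one common window, or a date on each row, the ambiguous minutes fall from 60 to 0.

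**The case against.** The best reply is that this form is not the only record. Table 1 lists documentation of all SBMs as routine nursing care, and Section 6.1 reserves the nursing form for data not routinely charted. The occurrence of a stool should therefore be recoverable from the clinical record. Investigators review the previous 24 hours each morning (Sections 5.7 and 9.2), the form has a line for the team member who verifies it, and case report forms are checked for completeness (Section 10). If the numbered rows are filled in time order, a 07:30 entry above a 10:00 entry reads differently from one below a 05:00 entry. Caregivers and investigators are blinded (Section 5.4.1), so errors should not differ by arm.

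Most of this stands and limits the size of the point. Three things remain. None of these steps is described as a reconciliation of dates, and a misdated stool looks complete. Row order is not instructed, and it cannot help when a form holds a single stool. Size and Bliss score are listed as non-routine, so for a stool left off the form the flowsheet may not supply the score that the diarrhea definition needs.

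A reader might infer that stools in this hour have no valid place and will be lost. The documents do not support that. A nurse who follows the table's own heading has a place for the entry on the previous day's form, and nothing says that form is closed or collected at 07:00. Double entry is as consistent with the instructions as omission.

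**Conclusion.** The inconsistency is real. Two windows on one page, with a single date per form, make one hour in 24 ambiguous by exactly 24 hours on the only study form that captures on-study SBM times. An uncorrected shift could change a primary event for a patient near 72 hours, and could alter time to first SBM, days without an SBM or the 24-hour diarrhea count.

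The likely effect is small. Under uniform timing and a first SBM in all 36 patients, about 1.5 first SBMs are expected to be exposed. Fewer would change an outcome, because an exposed entry must also be misdated, uncorrected and close to the threshold. A reader might take the 78% as the chance that a result is affected; it is only the chance that at least one first SBM falls in the hour under those two assumptions. No directional bias should be inferred either: under blinding the error should be noise. This is a minor correction to the data form and does not challenge the design or the analysis.

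**What to change.** Use one window for the form and its stool table. 07:00 to 06:59 matches the shift grid and Appendix 10 and so needs the fewest changes. Add a date to each stool row, as the baseline form already does for the last SBM before randomization.

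For forms already completed, and before unblinding, check every entry timed 07:00 to 07:59 against the ICU flowsheet. Also look in the flowsheet for stools charted in that hour that are missing from the forms or appear on two of them. Record the rule used to settle each case.

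The cost is a one-page form revision and a short chart check, with no change to the analysis. Version 19 is dated September 10, 2018 and Section 9.5 planned full enrollment by December 31, 2018. On that schedule the revised form would reach few patients, and the check of completed forms is the more useful part.

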Appendix 10. Investigative Team Daily Data Collection Form.

IRB # 12043 Impact of Naloxegol (Movantik) on Prevention of Lower Gastrointestinal Tract Paralysis in Critically Ill Adults Initiated on Scheduled IV Opioid Therapy: A Randomized, Double-Blind, Placebo-Controlled, Phase II, Single-Center, Proof of Concept Study. PI: [name]

Subject ID: _____ Subject Initials: _____ ICU Room: _____ *Date (of day shift): _____ Study day# _____

*Note: this monitoring form goes from 0700h to 06:59h the next day

Time frame	Day Shift (0700 – 14:59h)	Afternoon shift (15:00-22:59H)	Night shift (23:00-06:59h)
Fentanyl (mcg)			
Hydromorphone (mg)			
Morphine (mg)			
Oxycodone (mg)			
Hydrocodone (mg)			
Methadone (mg)			
Other Opioids: Name and Dose			
Diazepam (mg)			
Lorazepam (mg)			
Midazolam (mg)			
Dexmedetomidine (mcg)			

Drug Substance: Movantik
Study Number: ESR-15-11000
Tufts IRB #12043
Version: Protocol version #19
Date: September 10, 2018

Propofol (mg)			
Haloperidol (mg)			
Quetiapine (mg)			
Volume of enteral nutrition administered (mL)			
Enteral nutrition goal (mL)			
% of enteral nutrition goal reached			
Fluid balance (+ or -) (mL)			
Lowest SAS			
Highest SAS			
ICDSC score (if evaluated during this shift)			
Lowest pain assessment score			
Highest pain assessment score			
Current Laxative Guideline Step (ie. 1, 2, 3 or 4)			
Laxatives administered (list all agents and doses)			
Requirement for mechanical ventilation? (Y/N)			
Presence of rectal tube? (Y/N)			

Drug Substance: Movantik
Study Number: ESR-15-11000
Tufts IRB #12043
Version: Protocol version #19
Date: September 10, 2018

(Please note time of insertion if new)			
GI or Surgical consult for lower GI tract paralysis? Y/N			
SOFA Score (worst values over study day)			
Serum creatinine (worst value over study day)			
Calculated creatinine clearance (worst value over study day)			

initials of investigational team member completing/verifying form _____ **date** _____

Daily SOFA Calculator

Pt Study ID: Pt Initials:

PP MM

Please retain this worksheet at the site with the CRF.

Calculate SOFA score using values from the 24 hour period prior to randomization.

A. Please circle appropriate score

Drug Substance: Movantik
 Study Number: ESR-15-11000
 Tufts IRB #12043
 Version: Protocol version #19
 Date: September 10, 2018

Organ System	0	1	2	3	4	Score
RESPIRATION PaO ₂ /FiO ₂ (mmHg)	>400	301-400	201-300	101-200 with respiratory support	< 100 with respiratory support	
CARDIOVASCULAR Vasopressors (mcg/kg/min)	No hypotension	MAP < 70mmHg and No vasopressors	Dopamine ≤ 5 or Any dose Dobutamine	Dopamine > 5 or Epinephrine ≤ 0.1 or Norepinephrine ≤ 0.1	Dopamine >15 or Epinephrine > 0.1 or Norepinephrine > 0.1 or any dose Vasopressin	
LIVER (bilirubin) (mg/dl)	<1.2	1.2 – 1.9	2.0 – 5.9	6.0 – 11.9	≥ 12	
COAGULATION Platelets (x 10 ³ /µL)	>150	101-150	51-100	21-50	≤20	
RENAL Creatinine (mg/dL) or urine output mL/hr	<1.2	1.2 - 1.9	2.0 -3.4	3.5 – 4.9 or < 500 ml/day	≥ 5.0 or < 200 ml/day	
TOTAL SOFA=						

B. Please record below the actual values used in the scoring above.

PaO₂ |__|__|__|

Drug Substance: Movantik
Study Number: ESR-15-11000
Tufts IRB #12043
Version: Protocol version #19
Date: September 10, 2018

FiO₂ | | . | | |

MAP | | | |

Bilirubin | | | | μmol/L

Platelets | | | | x 10³/μL

Creatinine | | | | μmol/L or Urine output | | | | | mL/day

initials of investigational team member completing/verifying form _____ date _____

Drug Substance: Movantik
Study Number: ESR-15-11000
Tufts IRB #12043
Version: Protocol version #19
Date: September 10, 2018

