2. STUDY OBJECTIVES

Given that there is no one “gold-standard” way to characterize the efficacy of naloxegol to prevent lower GI tract paralysis in critically ill adults administered scheduled opioids, given the Phase II, proof of concept nature of this investigation we plan to consider multiple outcomes to evaluate naloxegol’s efficacy in this population. Since the original April 2015 protocol submission, in an effort to help better define those outcomes that are most relevant to clinicians when they are considering the efficacy (and safety) of a preventative strategy like naloxegol in their critically ill patients at risk for lower GI tract paralysis, we informally surveyed clinicians at Tufts Med Center (and elsewhere). Of note, time to the first spontaneous bowel movement (SBM) (which is directly related to our primary outcome of prevention of lower GI tract paralysis) was suggested most frequently as the most clinically relevant outcome when evaluating a new lower GI tract paralysis prevention intervention. Clinicians noted that once a patient receiving scheduled opioid therapy has their first SBM (and remained on any particular lower GI tract prophylaxis regimen) that the patient should ideally be expected to have a SBM at least daily. Therefore, these clinicians felt that comparing the ICU days without a SBM (noting that when 3 days without a SBM is met, the definition for lower GI tract paralysis is met) was also a clinically meaningful way to compare naloxegol with placebo. While most respondents questioned whether it was necessary (or even possible) to rigidly define a SBM (e.g., based on a specific fecal output volume), they suggested that we collect the following data for each SBM [1. Stool volume (i.e., small, medium or large) and 2. Stool consistency (i.e. using the Bliss stool scale score)] Clinicians generally felt that the other outcomes that were proposed in the previous version of this protocol (for both efficacy and safety) in April 2015 were all appropriate and should all be collected given the pilot nature of this investigation. With the recently published study by Palacio de Azeda et al [13] that found that the use of an aggressive daily lactulose and enema protocol reduced the average daily SOFA (organ severity) score, and that highlighted that there may be an important connection between lower GI tract paralysis and abdominal pressure, we would like to incorporate collection of daily SOFA scores and thrice daily measurement of abdominal pressure as an efficacy outcome in the study. Lastly, a recent paper found a strong relationship between delirium and lower GI tract paralysis in the critically ill and thus we propose to monitor each subject twice daily for delirium. [12].

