Measurement of bladder pressure in subjects with a foley catheter in place for a clinical reason (to estimate abdominal pressure) q8h		√	√	√	√	√	√	√	√	√	√	√	
Investigative team													
Requirement for mechanical ventilation	√	√	√	√	√	√	√	√	√	√	√	√	
SOFA score calculation (daily)		√	√	√	√	√	√	√	√	√	√	√	
Occurrence of lower GI tract paralysis requiring a GI or surgical consult		√	√	√	√	√	√	√	√	√	√	√	
Safety outcomes													
Monitoring that is a routine part of care at Tufts MC													
Bedside nurse													
Presence of diarrhea	√	√	√	√	√	√	√	√	√	√	√	√	
Investigative team													
Presence of a diaper or rectal tube		√	√	√	√	√	√	√	√	√	√	√	
Monitoring that is not a routine part of care at Tufts MC													
Bedside nurse													
Characterization of diarrhea using the Bristol Scale		√	√	√	√	√	√	√	√	√	√	√	
Evaluation for opioid withdrawal using the COWS scale before and 2 hours after each daily study dose		√	√	√	√	√	√	√	√	√	√	√	

Additional assessments not included in table:

1. Baseline demographics [age, gender, APACHE II score, Charlson comorbidity scale score, primary reason for ICU admission (based on APACHE III criteria)], baseline comorbidities potentially associated with an increased risk for lower gastrointestinal tract paralysis, treatments

Drug Substance: Movantik
Study Number: ESR-15-11000
Tufts IRB #12043
Version: Protocol version #19
Date: September 10, 2018

received at the time of ICU admission or administered after ICU admission that might influence SBM frequency and/or lower gastrointestinal tract paralysis incidence, and primary reason(s) for scheduled opioid initiation.

2. Evaluation for adverse events

Impact of Level of Sedation on Patient Assessments: Patients admitted to the Medical ICU at Tufts MC are generally maintained in an awake or lightly sedated state. For a patient who may require a short period of deeper sedation all of the following assessments above will be able to be still evaluated/collected **except:** COWS

Drug Substance: Movantik
Study Number: ESR-15-11000
Tufts IRB #12043
Version: Protocol version #19
Date: September 10, 2018

3.2 Rationale for study design, doses and control groups.

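### Appendix 10 gives two conflicting scoring windows for the daily SOFA score; separately, both SOFA worksheets mix measurement units

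*Protocol*

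**What the plan says.** Protocol section 2 states the intention: "we would like to incorporate collection of daily SOFA scores and thrice daily measurement of abdominal pressure as an efficacy outcome in the study". Table 1 (section 3.1) lists "SOFA score calculation (daily" among the efficacy outcomes, as a task for the investigative team.

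Appendix 10 is the form on which that team collects its daily data (section 6.1). It has two parts that bear on SOFA:

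- The daily form has a study-day number and states that "this monitoring form goes from 0700h to 06:59h the next day". Its SOFA row reads "SOFA Score (worst values over study day".
- The Daily SOFA Calculator follows. Its instruction is "Calculate SOFA score using values from the 24 hour period prior to randomization".

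Appendix 11 gives the same pre-randomisation instruction for the baseline SOFA score, where it fits.

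On units, part A of the calculator is a scoring grid with rows headed "LIVER (bilirubin) (mg/dl" and "RENAL Creatinine (mg/dL) or urine output mL/hr". Part B asks for the values that were used in part A, but prints micromol/L beside bilirubin and creatinine. For urine output, the grid cells and the part B field are per day, although the row header is per hour. The Baseline SOFA Calculator in Appendix 11 has the same layout and the same mismatches.

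**The concern.** A daily score needs a scoring window that moves with the study day. The worksheet that produces the score names a fixed window ending at randomisation, while the form that receives it names the study day. A data collector has two incompatible instructions on adjacent pages of one appendix. Section 11.1, which should define how efficacy variables are derived, only points back to Table 1 and the objectives, and neither gives a window.

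A daily SOFA series scored on pre-randomisation values cannot register any change after treatment starts. Section 1.2 says the study is meant to show how candidate endpoints behave and vary, to inform larger trials. A series in which some collectors use one window and some the other would not serve that purpose.

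The unit mismatch is a different fault with a different consequence. It can produce a wrong organ score, or a correct score beside a raw value that cannot be verified against the laboratory record.

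**Working it through.** The documents state no sample size, power or alpha for SOFA, so there is no plan figure to reproduce. The window question is a comparison of text; the unit question allows a small calculation.

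**Step 1: the window**

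| Place | Window for the score |
|---|---|
| Appendix 10, daily form, SOFA row | Worst values of the study day (form runs 07:00 to 06:59) |
| Appendix 10, Daily SOFA Calculator | 24 hours before randomisation |
| Appendix 11, item 15 and Baseline SOFA Calculator | 24 hours before randomisation |
| Table 1 | Daily; no window given |
| Section 11.1 | Refers to Table 1 and the objectives |

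Let B be the score from the 24 hours before randomisation and S(d) the score from the worst values of study day d.

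- Calculator followed literally: daily score = B for every d, so change = B − B = 0 on each of up to 10 days, in either arm.
- Form row followed: change = S(d) − B, as a daily outcome requires.
- Mixed practice: some changes are 0 by construction and others are real, and the score alone does not show which.

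**Step 2: bilirubin and creatinine units**

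Inputs from the grid, in mg/dL:

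| Score | 0 | 1 | 2 | 3 | 4 |
|---|---|---|---|---|---|
| Bilirubin | <1.2 | 1.2–1.9 | 2.0–5.9 | 6.0–11.9 | ≥12 |
| Creatinine | <1.2 | 1.2–1.9 | 2.0–3.4 | 3.5–4.9 | ≥5.0 |

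Assumption, not in the documents: 1 mg/dL is about 17.1 micromol/L for bilirubin and about 88.4 micromol/L for creatinine.

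The worst case is a micromol/L value read directly against the mg/dL cells:

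| True value | In micromol/L | Correct score | Misread score |
|---|---|---|---|
| Bilirubin 0.5 mg/dL | 0.5 × 17.1 = 8.6 | 0 | 3 |
| Bilirubin 1.0 mg/dL | 17.1 | 0 | 4 |
| Bilirubin 1.9 mg/dL | 1.9 × 17.1 = 32.5 | 1 | 4 |
| Creatinine 0.6 mg/dL | 0.6 × 88.4 = 53.0 | 0 | 4 |
| Creatinine 1.0 mg/dL | 88.4 | 0 | 4 |
| Creatinine 1.9 mg/dL | 1.9 × 88.4 = 168.0 | 1 | 4 |

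The largest error is 4 + 4 = 8 points. The grid has 5 organ systems scored 0 to 4, so its maximum is 5 × 4 = 20, and 8/20 = 40% of the scale. In the best case staff score in mg/dL and the mismatch affects only what is written in part B; the scoring error is then 0.

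The misread score saturates quickly. Bilirubin reads as 4 from 12/17.1 = 0.70 mg/dL upward, and creatinine from 5/88.4 = 0.057 mg/dL upward. A consistent misreading would therefore hold the renal component at 4 for practically any patient and hide real change in that organ.

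**Step 3: urine output**

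The renal cells use <500 ml/day (score 3) and <200 ml/day (score 4). An hourly figure entered as the header suggests and compared with those cells would score 4 whenever it is below 200 mL/hr, that is, below 200 × 24 = 4,800 mL/day. Creatinine and urine output share one renal score capped at 4, so this is a second route to the same 4 points and does not raise the maximum above 8.

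**Step 4: what depends on the score**

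SOFA is named in section 2 and in Table 1. It is absent from the secondary objectives (2.2), the efficacy variable list (6.3.1), the analysis methods (12.2) and the SAP. The power table concerns failure to defecate by day 4.

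**The case against.** The best defence is that the intended window is obvious. The calculator feeds a row on the same form labelled with the study day, the form covers a defined 24-hour period, and Table 1 calls for a daily calculation. The calculator's sentence matches the one on the baseline worksheet and was most likely carried over. Trained members of the investigative team complete the form (sections 6.1 and 9.4), and section 10 has case report forms checked for completeness. On units, scores are circled in part A before values are copied to part B. Creatinine on the APACHE II sheet and bilirubin in the Child-Pugh table are both in mg/dL, so the likelier error is a right score with a wrongly labelled raw value.

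Most of this stands. It makes the study-day reading the likely intention and the large unit error the less likely outcome. It does not remove the contradiction: the worksheet is kept with the case report form, carries its own completion and verification line, and states a rule that gives a wrong daily score if obeyed. A completeness check would not detect a completed score taken from the wrong window. The documents do not state the laboratory's reporting units.

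A reader might go further and infer three things that the documents do not support:

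- That daily SOFA will repeat baseline in every patient. This needs every collector to ignore the form row every day, and nothing shows that this happened.
- That the mixed units contribute to that repetition of pre-randomisation values. They do not; they are a separate route to a wrong score, and the baseline worksheet shares them.
- That a planned efficacy comparison is lost. No comparison of SOFA is specified in section 12.2 or the SAP.

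**Conclusion.** The point holds as an internal contradiction in a data-collection instruction, with a separate unit fault on both worksheets.

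- **Window:** the effect depends on which instruction was followed. It is nil if the form row was used. If the calculator was used literally, change from baseline is 0 by construction on up to 10 days.
- **Units:** the scoring error from the bilirubin and creatinine mismatch lies between 0 and 8 points out of 20. The upper end rests on assumed conversion factors and on micromol/L values being read against mg/dL cut-points. The documents do not show where in that range practice fell.
- **Reach:** limited to daily SOFA for the window, and to daily and baseline SOFA for the units. The primary outcome, sample size and power are untouched.

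It should be corrected because the protocol presents daily SOFA as an efficacy outcome, no other section resolves the conflict, and the correction is already available in the protocol's own form. It is a form inconsistency of modest consequence and no threat to the trial's main conclusion.

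**What to change.** 1. On the Daily SOFA Calculator, replace the pre-randomisation instruction with the window of the daily form's SOFA row: worst values over the study day, 07:00 to 06:59.
2. Keep the 24 hours before randomisation on the baseline form and Baseline SOFA Calculator only.
3. On both worksheets, use one unit per variable throughout: the same unit for bilirubin and for creatinine in the grid and in part B, and the same time base for urine output in the renal header, the cells and part B.
4. Check completed daily and baseline worksheets against the chart. Re-score only those where the wrong window or unit was used, and do so before treatment codes are released.
5. If daily SOFA is to be reported as an outcome, add it to sections 2.2 and 6.3.1 and give it an analysis in section 12.2 and the SAP.

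Items 1 to 3 are a form correction. Item 4 costs a check of existing worksheets for at most 36 patients and 10 study days each (36 × 10 = 360 daily sheets, plus 36 baseline sheets), with re-abstraction only where an error is found. The section 9.5 timetable puts first enrolment in May 2017 and this protocol version is dated September 2018, so some worksheets may already be complete.
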